7.8 Adverse Events Monitoring

All adverse events, whether or not unexpected, and whether or not considered to be associated with the use of the study drug, will be entered into OnCore[®], as noted above.

The Investigator will assess all adverse events and determine reportability requirements to the UCSF Data and Safety Monitoring Committee (DSMC) and UCSF's Institutional Review Board (IRB); and, when the study is conducted under an Investigational New Drug Application (IND), to the Food and Drug Administration (FDA) if it meets the FDA reporting criteria..

All adverse events entered into OnCore[®] will be reviewed by the Helen Diller Family Comprehensive Cancer Center Site Committee on a weekly basis. The Site Committee will review and discuss at each weekly meeting the selected toxicity, the toxicity grade, and the attribution of relationship of the adverse event to the administration of the study drug(s).

In addition, all adverse events and suspected adverse reactions considered “serious,” entered into OnCore® will be reviewed and monitored by the Data and Safety Monitoring Committee on an ongoing basis and discussed at DSMC meetings which take place every six (6) weeks. For a detailed description of the Data and Safety Monitoring Plan for a Multicenter Study refer to Appendix 9.

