8.3 Determination of Sample Size and Accrual Rate

8.3.1 Sample Size and Power Estimate

The sample size for this single-arm phase II study is based upon the anticipated degree of improvement in the primary clinical hypothesis (i.e. local-regional control rate) at 12 months after completing all protocol treatment. The null hypothesis is that 60% of patients treated may achieve local-regional control after treatment on the study. Patients treated for advanced-stage

nonmelanomatous skin cancers typically achieve 50-60% local-regional control with radiation therapy alone. The alternative hypothesis is that 80% of the patients will obtain local-regional control at 12 months from the end of protocol therapy. This goal for local-regional control is justifiable as the current study includes radiation therapy, which is known to be effective against advanced BCC, in combination with vismodegib, also known to have high efficacy against BCC when administered alone.

Sample Size Justification: With accrual of 24 evaluable patients, this test will have 81% power to detect an increase in the overall proportion of patients achieving local-regional control assuming a directional level of significance of 0.10 based upon a one sample exact binomial test. It is anticipated that accrual will be completed in 12-18 months, with each patient treated for approximately 5.5 months and then followed for 12 months after completing protocol therapy. The total study duration is expected to be about 3 years.

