8.4 Interim Analysis for Safety and Stopping Rules

An interim analysis for safety will be performed once 5 patients have been treated on study and completed all drug and radiation-based protocol therapy. This will occur approximately 7-8 months after the start of accrual assuming 2 patients are enrolled per month and protocol therapy is completed in about 5.5 months. After the fifth patient completes radiation therapy, accrual will be temporarily stopped in order to perform this interim analysis. Thus no additional patients will start radiation therapy during the evaluation interval that overlaps with the treatment period for patients included in the interim analysis. During the conduct of this study, toxicity will also be evaluated weekly so that any unacceptable toxicity can be identified early. If there is no reason to stop accrual (as defined below), the remainder of the 19 patients will be recruited.

Stopping rules: Acceptable occurrence of toxicity is defined as the discontinuation of treatment in $\leq 40\%$ of patients (2 of 5 patients who discontinue protocol treatment, having completed $< 75\%$ of planned radiation therapy) and the proportion of patients with grade 4-5 toxicity is $\leq 20\%$.

Accrual of the final 19 patients will be determined by the results of the interim analysis.

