If an increase in the frequency of Grade 3 or 4 adverse events (above the rate reported in the Investigator Brochure or package insert), the Study Chair at the UCSF Coordinating Center is responsible for notifying the DSMC at the time the increased rate is identified. The report will indicate if the incidence of adverse events observed in the study is above the range stated in the Investigator Brochure or package insert.

If at any time the Study Chair stops enrollment or stops the study due to safety issues, the DSMC Chair and DSMC Manager must be notified within 1 business day via e-mail. The DSMC must receive a formal letter within 10 business days and the IRB must be notified.

Data and Safety Monitoring Committee Contacts:

DSMC Chair:
Phone:
Email:
Address:

DSMC Monitors

* DSMP approved by NCI 09/February2012

Appendix 10 UCSF Policy/Procedure for Required Regulatory Documents for a UCSF Multicenter Investigator-Initiated Oncology Clinical Trials with an Investigator held Investigational New Drug (IND)

Purpose

This policy defines the required Regulatory Documents for Single Site and Multicenter Investigator Initiated Oncology Clinical Trials at the Helen Diller Family Comprehensive Cancer Center (HDFCCC) where the Principal Investigator (PI) holds the IND.

Background

The International Conference on Harmonization (ICH) Good Clinical Practices (GCP) Guidelines define Essential Regulatory Documents as those documents which individually and collectively permit evaluation of the conduct of a trial and the quality of data produced. These documents serve to demonstrate compliance with standards of GCP and with all applicable regulatory requirements. Filing essential documents in a timely manner can greatly assist in the successful reconscilimangement of a clinical trial.

The Regulatory Documents will consist of electronic files in both iMedRIS and OnCore[®], as well as paper files in the Regulatory Binders for both the Coordinating Site and the Participating Site(s) in the HDFCCC Investigator Initiated Oncology Clinical Trials.

Procedures

1. HDFCCC Essential Regulatory Documents

Documents Filed in iMedRIS:

- IRB approvals for initial submission of application, all modifications, and continuing annual renewals
- Current and prior approved protocol versions with signed protocol signature page(s)
- Institutional Review Board (IRB) approval letters and Informed Consent Form(s) (ICF)
- Current and prior versions of the Investigator Brochure (IB).

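### The numeric toxicity limits are applied once, to the first 5 patients; for the other 19 there is oversight but no count or rate that pauses accrual

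*Combined protocol and SAP*

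**What the plan says.** Section 8.4 provides for one look: "An interim analysis for safety will be performed once 5 patients have been treated on study" and have finished all protocol therapy. Toxicity is acceptable if no more than 40% of patients (2 of 5) discontinue with less than 75% of planned radiation delivered, and no more than 20% have grade 4-5 toxicity, which is 1 of 5. The consequence is stated as "Accrual of the final 19 patients will be determined by the results of the interim analysis".

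The following also applies to later patients:

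- Section 8.4: "toxicity will also be evaluated weekly so that any unacceptable toxicity can be identified early". Unacceptable is not given a number outside the look at 5.
- Section 7.8: the Site Committee reviews adverse events weekly (Appendix 9 says monthly for grade 3-5 events). Serious events are "discussed at DSMC meetings which take place every six (6) weeks".
- Appendix 9: if grade 3 or 4 events exceed the rate in the brochure or package insert, the Study Chair "is responsible for notifying the DSMC at the time the increased rate is identified". No figure is given and no pause follows.
- Section 7.9 and Appendix 9: a related death on treatment or within 30 days of the last dose goes to the DSMC Chair, within 1 business day of each notification step.
- Appendix 9 also recognises that the Study Chair may stop enrolment for safety at any time.

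Section 5.3.1 concerns stopping the drug in one patient and is not a study-level limit.

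**The concern.** A rule on 5 patients has little power to tell an acceptable toxicity rate from one well above the plan's own limit. A trial that passes by chance then has 19 of its 24 patients (79%) still to come, and the 20% and 40% figures are not tied to any later decision. Weekly and six-weekly reviews will see the events, but the people reviewing them have no agreed count at which to pause.

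Two features add weight. The protocol cites no earlier clinical data on the combination: Section 1.3 rests on preclinical evidence, and Section 4.2 says wound-healing effects may be intensified. Also, Section 8.2 tabulates toxicity for up to 12 months after therapy, whereas the look takes place when the fifth patient finishes radiation. Later events, even in those first five, are not compared with the 20% limit.

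**Working it through.** **Inputs.** Look at 5 patients, grade 4-5 limit 20%, discontinuation limit 40%, 19 patients to follow (all Section 8.4); 24 evaluable patients (Section 8.3.1); therapy about 5.5 months (Sections 8.3.1 and 8.4); 1-2 patients per month (Section 8.3.3). The true toxicity rates p are assumptions, shown as a range.

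**The plan's own figure.** The plan gives no operating characteristics for the safety rule. Its one stated design figure is for efficacy: "With accrual of 24 evaluable patients, this test will have 81% power". Exact binomial, success at 18 or more of 24: alpha 0.0960 at 60%, power 0.8111 at 80%. The 81% reproduces.

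**Passing the grade 4-5 condition.** P(at most 1 of 5) = (1−p)^5 + 5p(1−p)^4.

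- p = 10%: 0.5905 + 0.3281 = 91.9%
- p = 20%: 0.3277 + 0.4096 = 73.7%
- p = 30%: 0.1681 + 0.3602 = 52.8%
- p = 40%: 0.0778 + 0.2592 = 33.7%

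**Adding the discontinuation condition.** At p = 40%, multiply 0.337 by P(at most 2 of 5 discontinue), assuming independence. For discontinuation rates of 10%, 20%, 30% and 40% the joint pass probability is 33.4%, 31.7%, 28.2% and 0.337 × 0.6826 = 23.0%. If only patients with grade 4-5 events discontinue, it stays at 33.7%. So 33.7% is the upper bound for the full rule.

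**After a pass at 40%.** The first five contribute 0.2592/0.337 = 0.77 patients with events on average, and the other 19 contribute 19 × 0.4 = 7.6. The total is about 8.4 of 24 if accrual is not paused.

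**A calibrated later boundary.** At each patient number from 8 to 24, take the smallest count whose upper-tail probability at p = 20% is no more than 0.11. This gives 4 patients with grade 4-5 toxicity at 8-9, 5 at 10-13, 6 at 14-17, 7 at 18-21 and 8 at 22-24. After a pass there are at most 2 events by patient 6 and 3 by patient 7, so entries before patient 8 would matter only if a late event arose in the first five. Exact recursion over patients 6-24, with each outcome known before the next patient enters and late events ignored:

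| True rate | Passes look at 5 | Pauses later, given a pass | Never pauses | Total halt chance, both stages |
|---|---|---|---|---|
| 10% | 91.9% | 0.5% | 91.4% | 8.6% |
| 20% | 73.7% | 9.5% | 66.7% | 33.3% |
| 30% | 52.8% | 38% | 32.7% | 67.3% |
| 40% | 33.7% | 72% | 9.3% | 90.7% |

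**Repeating the raw 20% cut-off instead.** Rechecking at 10, 15 and 20 patients (at most 2, 3 and 4 events) lowers the chance of never crossing at a true 20% from 73.7% to 47.9%. That halts too often at the plan's own limit, so later looks need their own calibration.

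**Outcome lag.** With the first patient at month 0 and 2 per month, the fifth enters at month 2 and finishes at 2 + 5.5 = 7.5 months; by then 2 × 7.5 + 1 = 16 patients have enrolled. At 1 per month, the fifth finishes at 4 + 5.5 = 9.5 months, with 10 enrolled.

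**The case against.** Five points deserve an answer.

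- **Oversight exists.** A reader might infer that patients 6-24 have no safety protection. The documents do not support that: weekly evaluation, Site Committee review, DSMC review of serious events, the brochure-rate notice and the power to stop enrolment all apply to them. What is absent is a numeric study-level pause.
- **Deaths are handled.** A reader might also infer that a treatment-related death could pass unexamined because 1 of 5 is exactly 20%. Related deaths on treatment or within 30 days already go to the DSMC Chair. What remains is that this notice is not linked to an accrual decision, and that later related deaths fall outside it.
- **The 20% may be meant throughout.** Section 8.4 attaches 2 of 5 only to discontinuation and states the grade 4-5 limit as a proportion without a denominator, so it could be read as governing the weekly review too. The sentence on the final 19 patients favours the single-look reading. If the wider reading was intended, a calibrated boundary is still needed.
- **A 40% rate is not predicted.** With the drug alone, Section 1.2.1 reports no dose-limiting toxicities and Section 1.2.2 reports related serious events in 4%. Section 4.2 expects no synergistic overlap except possibly in wound healing. That is fair: 30% and 40% are stress values, not forecasts.
- **The boundary is modest and its benefit is reduced by lag.** It lets 7 of 24 (29%) through, and at a true 30% about 62% of trials that pass the first look never trigger it. At a true 40% the mean trigger is at patient 14.7. If outcomes were known only at the end of therapy and accrual ran at 2 per month, essentially all 24 would already be enrolled. Counting events as they occur shortens this delay but does not remove it.

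**Conclusion.** The point holds as a gap in the stopping rule. The only numeric study-level limits are applied once, to 5 patients, and no later count or rate pauses accrual. At assumed true grade 4-5 rates of 30% and 40%, the grade 4-5 condition passes 53% and 34% of the time. The second figure is the ceiling for the full rule, which passes about 23% of the time with an independent 40% discontinuation rate.

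Two stronger statements should not be made. The one-in-three figure does not describe the whole look under every discontinuation rate. The fall from 34% to 9% is a change in the chance of crossing a line under immediate reporting, not a number of patients spared. The results assume independent patients and a constant event rate.

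**What to change.** Keep the look at 5. Add a short table to Section 8.4 under which accrual pauses for DSMC review, without terminating the study, when the cumulative number of patients with grade 4-5 toxicity reaches, for example, 4 by patient 8-9, 5 by 10-13, 6 by 14-17, 7 by 18-21 or 8 by 22-24. Apply it at the existing weekly review, count events as they occur, and include late events in the first five. State whether the 20% and 40% figures have any role after patient 5, and reconcile the weekly and monthly Site Committee schedules in Section 7.8 and Appendix 9.

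On grade 5, add only that the existing death notice to the DSMC Chair, and any later related death, also prompts an accrual decision, so that 1 of 5 does not count as acceptable by percentage alone.

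A discontinuation boundary against 40% should be added only after its own calibration, including its joint false-pause rate with the toxicity boundary.

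**Cost.** One table and a sentence or two. At a true 20%, the chance of a pause after passing the first look is 9.5%, or 7 percentage points unconditionally (0.737 × 0.095), which takes the total halt chance from 26% to 33%. At a true 10%, the chance of a pause after a pass is 0.5%.

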7.6 Recording of an Adverse Event

All grade 3 and above adverse events will be entered into OnCore[®], whether or not the event is believed to be associated with use of the study drug. Data about these events and their severity will be recorded using the NCI CTCAE v4.0.

The Investigator will assign attribution of the possible association of the event with use of the investigational drug, and this information will be entered into OnCore[®] using the classification system listed below:

Relationship	Attribution	Description
Unrelated to investigational drug/intervention	Unrelated	The AE is clearly NOT related to the intervention
	Unlikely	The AE is doubtfully related to the intervention
Related to investigational drug/intervention	Possible	The AE may be related to the intervention
	Probable	The AE is likely related to the intervention
	Definite	The AE is clearly related to the intervention

Signs or symptoms reported as adverse events will be graded and recorded by the Investigator according to the CTCAE v 4.0. When specific adverse events are not listed in the CTCAE v 4.0 they will be graded by the Investigator as *none, mild, moderate* or *severe* according to the following grades and definitions:

- Grade 0 No AE (or within normal limits)
- Grade 1 Mild; asymptomatic or mild symptoms; clinical or diagnostic observations only; intervention not indicated
- Grade 2 Moderate; minimal, local, or noninvasive intervention (e.g., packing, cautery) indicated; limiting age-appropriate instrumental activities of daily living (ADL)
- Grade 3: Severe or medically significant but not immediately life-threatening; hospitalization or prolongation of hospitalization indicated; disabling; limiting self-care ADL
- Grade 4: Life-threatening consequences; urgent intervention indicated
- Grade 5: Death related to AE

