7.9 Expedited Reporting

Participating sites reporting to Study Chair

In addition to complying with all applicable regulatory reporting laws and regulations, each site will report the following information in writing to the Sponsor-Investigator within one business day of the Investigator’s awareness of occurrence:

- All SAEs
- Reports of pregnancy exposure (pregnancy encompasses the entire course of pregnancy and delivery, perinatal and neonatal outcomes, even if there were no abnormal findings; both maternal and paternal exposure is collected);
- Reports of lactation exposure;
- Overdose (with or without an SAE);
- Abuse (use for non-clinical reasons with or without an SAE);
- Inadvertent or accidental exposure; and
- Follow-up information regarding any of the above.
- The participating investigator should include his or her assessment of the causal relationship between each SAE and the study treatment.

Death from any cause while a patient is receiving protocol treatment and up to 30 days after the end of protocol must be telephoned and reported within ten days of discovery. Death related to surgery, regardless of the interval from surgery, must be reported by telephone within 10 days of discovery.

Reports will include the cover page provided, and reference the Protocol Number.

A copy of the report should be sent to the coordinating center CRC at UCSF. Information will be provided.

Reporting to the Data and Safety Monitoring Committee

If a death occurs during the treatment phase of the study or within 30 days after the last administration of the study drug(s) and it is determined to be related either to the study drug(s) or to a study procedure, the Investigator or his/her designee must notify the DSMC Chair (or qualified alternate) within 1 business day of knowledge of the event. The contact may be by phone or e-mail.

Reporting to UCSF Committee on Human Research (Institutional Review Board)

The Principal Investigator must report events meeting the UCSF IRB definition of “Unanticipated Problem” (UP) within 10 business days of his/her awareness of the event.

Reporting to Genentech or Roche

Study investigators must report all SAEs to Genentech or Roche within the timelines described below. The completed IND Safety Reports submitted to the FDA/Medwatch/case report should

be faxed immediately upon completion to Genentech Drug Safety at:

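### Section 8.4's pooled, inclusive 20% limit on grade 4-5 toxicity lets exactly one toxic death in the first five patients count as acceptable, and no rule requires a pause after a related death

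*Combined protocol and SAP*

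**What the plan says.** Section 8.4 plans one safety interim, after five patients have been treated. Toxicity is acceptable when no more than 40% (2 of 5) discontinue before 75% of planned radiation "and the proportion of patients with grade 4-5 toxicity is" at most 20%. Grades 4 and 5 share that single limit. Section 7.6 gives the top grade as "Grade 5: Death related to AE".

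The consequence of passing is explicit: "If there is no reason to stop accrual (as defined below), the remainder of the 19 patients will be recruited". The only mandated halt is tied to the calendar of the fifth patient, not to an event: "After the fifth patient completes radiation therapy, accrual will be temporarily stopped in order to perform this interim analysis".

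Other oversight exists:
- **Section 8.4:** "toxicity will also be evaluated weekly so that any unacceptable toxicity can be identified early". No threshold or required action is attached.
- **Section 7.8:** the Site Committee reviews adverse events, and serious events are "monitored by the Data and Safety Monitoring Committee on an ongoing basis and discussed at DSMC meetings which take place every six (6) weeks".
- **Section 7.9 and Appendix 9:** sites report SAEs within one business day. The DSMC Chair gets one-business-day notice of a related death during treatment or within 30 days of the last dose. Unanticipated problems go to the IRB.
- **Section 7.4:** reporting to the FDA and IRBs under the IND safety rules.
- **Appendix 9:** describes what follows if the Study Chair stops enrollment for safety, without saying when that must happen.

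**The concern.** A limit that pools grades 4 and 5 treats a toxic death like a reversible life-threatening event. Because the limit is inclusive and the look has five patients, one event sits exactly on the boundary and passes. The prespecified rule then says to continue in a curative-intent trial, and anyone who thinks otherwise must act outside it.

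Before the interim stop and after it, new patients can enroll and induction patients can start radiation while a related death is under review, because any hold is a matter of judgment. Section 4.2 says wound-healing effects of radiation may be intensified by vismodegib. It also says that, without further surgery, serious additional wound-healing toxicity is not expected, and that these effects will be tracked. The case therefore rests on the limited experience with the combination and on the wording of the rule, not on a predicted excess of deaths.

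**Working it through.** **The plan's own figure.** The interim rule states no operating characteristics. The one computed design figure, 81% power in section 8.3.1, reproduces: success at 18 or more of 24 gives exact one-sided alpha 0.096 at 60% and power 0.811 at 80%. It does not bear on this point.

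**Step 1: the rule applied to counts.**
- One death, no other grade 4-5 patient: 1/5 = 20%, which meets the limit.
- If that patient also stopped before 75% of radiation: 1/5 = 20% discontinuing, within 40%. Both conditions still pass.
- Two deaths, or one death plus grade 4 toxicity in another patient: 2/5 = 40%, which fails.

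**Step 2: how likely the scenario is.** Let p be the related-death rate by the interim and q the grade 4 risk in a patient who does not die. The documents give neither for the combination, so both are assumed. For drug alone, section 1.2.2 reports no death judged related among 104 patients; the one-sided 95% upper bound is 1 - 0.05^(1/104) = 2.8%. That makes 1-2% a reasonable range and 5-10% pessimistic.

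P(one death in five and limit met) = 5p[(1-p)(1-q)]^4

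| p | q = 0 | q = 10% | q = 20% |
|---|---|---|---|
| 1% | 0.048 | 0.032 | 0.020 |
| 2% | 0.092 | 0.061 | 0.038 |
| 5% | 0.204 | 0.134 | 0.083 |
| 10% | 0.328 | 0.215 | 0.134 |

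These figures also require no more than two of five discontinuing. They assume that a patient who dies counts among the five, and they fall if some deaths come after the interim.

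**Step 3: what an event-triggered pause would cost.** Only deaths while accrual is open pause accrual. Take entry as uniform over A months (12 to 24, from sections 8.3.1 and 8.3.3). Take death time as uniform over T months: 5.5 for treatment only, 17.5 for treatment plus 12 months' follow-up. The share f of deaths in the open window is 1 - T/(2A) when T is at most A, and A/(2T) otherwise.
- Lowest: A = 12, T = 17.5, f = 12/35 = 0.343.
- Highest: A = 24, T = 5.5, f = 1 - 5.5/48 = 0.885.

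P(at least one pause) = 1 - (1 - pf)^24

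| p | f = 0.343 | f = 0.885 |
|---|---|---|
| 1% | 0.079 | 0.192 |
| 2% | 0.152 | 0.349 |
| 2.9% (3/104) | 0.21 | 0.46 |

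The last row covers a trigger that includes possibly related deaths. In the drug-alone trial three of the seven deaths were of unknown cause; all seven were judged unrelated, so rating those three as possible is an assumption. With four replaced patients (also assumed; 28 at risk), the 1% and 2% rows become 0.092 to 0.220 and 0.175 to 0.394.

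**The case against.** The strongest reply is that a related death cannot pass quietly. It reaches the Study Chair, Site Committee, DSMC, IRB and FDA, and the Study Chair can stop enrollment at once. Section 8.4 also keeps further patients from starting radiation during the interim evaluation. On this view the gap is only that a pause is judged rather than automatic, and at 1-2% the scenario is uncommon. That stands, and it limits the point to a cheap improvement. It does not remove the fact that the one written rule says to continue.

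Three stronger readings are tempting and should not be adopted.

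- **A running 20% limit.** A reader might apply 20% to every later patient count and conclude that several deaths would be tolerated by the end. The protocol states no such rule: the figure belongs to the five-patient look, and the weekly evaluation has no number.
- **Many patients exposed before the interim.** Section 8.4 says of the look: "This will occur approximately 7-8 months after the start of accrual assuming 2 patients are enrolled per month". Multiplying gives 2 x 7-8 = 14-16 enrolled. That overstates exposure to the combination. Radiation starts about week 15, roughly 3.2 months after entry, so about 2 x (7 - 3.2) = 8 to 2 x (8 - 3.2) = 10 would have begun it. Two per month is also the top of the range in section 8.3.3, and 8.4 itself speaks of 19 still to recruit.
- **Expected serious wound-healing harm.** Section 4.2 says the opposite of expected, and does not link wound healing to deaths.

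One ambiguity remains. Section 8.4 times the look on five patients who completed all therapy, so a patient who dies during treatment might not be counted. The discontinuation criterion makes sense only if non-completers count, which supports counting the death, but the text does not settle it.

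**Conclusion.** The point holds. Exactly one toxic death in the first five patients, with no other grade 4-5 patient and no more than two of five discontinuing, is classed as acceptable and releases the remaining 19. No provision requires a pause or a different interim decision after a related death; the others notify, review or leave a stop to discretion.

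The scenario has probability of about 2-9% at assumed related-death rates of 1-2%. The upper end needs no grade 4 risk in the other four patients, and the whole range depends on counting a patient who dies among the five. A reader might infer that deaths would go unnoticed or that the trial lacks safety oversight; the reporting provisions contradict that.

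**What to change.** Keep the pooled 20% limit and add to section 8.4:

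> In addition, any grade 5 event assessed as possibly, probably or definitely related to vismodegib or radiation, in any patient who received study drug, whether or not therapy was completed, pauses new enrollment, and the start of radiation in patients still in induction for no longer than the delay 6.1.2.3 allows, until the DSMC has reviewed it in an expedited (ad hoc) review; a grade 5 event is not classed as acceptable at the interim without that review.

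Extend the one-business-day DSMC Chair notice in section 7.9 and Appendix 9 to related deaths in follow-up.

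The radiation clause is needed because an enrollment pause alone would not stop induction patients from moving to combined treatment. The review must be ad hoc because six-weekly meetings are too slow: section 6.1.2.3 asks investigators to consider removing a patient once the radiation start is delayed over four weeks. Radiation already under way continues, in line with section 5.3.

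The change uses the existing DSMC and SAE reporting, and related grade 4-5 events through follow-up are already an endpoint (section 2.3.2). Sample size and endpoints do not change. The downside is the accrual pause: about 8-19% probability at a 1% related-death rate, 15-35% at 2% and 21-46% at 2.9%. Its length depends on how quickly the DSMC reviews, so it cannot be promised to be short. These figures cover the accrual pause only; a hold on radiation starts could also occur while the last enrolled patients are in induction.
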